6.2.3 Dose Preparation and Administration

Study drug (PTG-100 or placebo) will be administered by subjects orally QD.

Matching PTG-100 (150-mg or 300-mg capsule) and placebo capsules will be provided to subjects in prepackaged individual study drug wallet kits, identical in appearance, according to the randomisation schedule. Each prepackaged kit will be appropriately labelled. Each day during the double-blind treatment period (preferably in the morning), subjects will take a total of 3 capsules, without regard to meals, according to their blinded treatment assignment, as follows:

- 150 mg PTG-100 group will receive: 1 × 150-mg capsule, 2 × placebo capsules
- 300 mg PTG-100 group will receive: 2 × 150-mg capsules, 1 × placebo capsule
- 900 mg PTG-100 group will receive: 3 × 300-mg capsules
- Placebo group will receive: 3 × placebo capsules

Study drug will be prepared in blinded blister packs and dispensed by the pharmacist (or appropriate designee) at study site visits; the subject will return any unused study drug at site visits during which site personnel will record used and unused capsules.

Subjects will be encouraged to take their daily study drug in the morning at approximately the same time each day. If the subject forgets to take a morning dose, the subject will be advised to take the dose on the same day. If it has been more than 12 hours since they were due to take the dose, they will be advised to skip that dose and resume the daily schedule with the next dose. Subjects will be told to not “double-up” on the doses if doses are missed.

All study personnel including the Sponsor, Contract Research Organization (CRO), Medical Monitors, Investigator, site pharmacist (or designee), site personnel involved in

study conduct, and subjects will remain blinded to study medication assignment. Appropriate unit doses, as described above, will be administered to consecutively-numbered subjects.

For all site visit days, doses will be administered orally after PK and PD blood collections. Doses will be preceded by an overnight fast (ie, at least 8 hours) from food (not including water) on Days 0, 28, 84, and 112 only prior to safety lab collection. Subjects may resume food after the blood collection.

At all other times during the study, subjects will have no water or meal restrictions or requirements.

6.2.4 Blinding

This will be a double-blind, placebo-controlled study. As such, the Sponsor, CRO, Medical Monitors, Investigator, site pharmacist (or designee), site personnel involved in study conduct, and subjects will remain blinded to study medication assignment.

An independent Data Monitoring Committee (DMC) will monitor safety throughout the study period and may be unblinded as necessary. Limited personnel required for conducting the analyses may also be unblinded to allow necessary safety oversight. The DMC will also be involved in the IA. Limited personnel required for conducting the IA will also be unblinded. Unblinded personnel required for the IA will be defined in the DMC charter.

Unblinding of individual subject treatment assignment may be permitted in the event of an emergency situation requiring knowledge of treatment assignment; however, subject assignment should not be routinely unblinded. Unblinding will be performed via the IXRS. This randomisation information may be opened and the randomisation for each individual subject made available to the Investigator (or designee) only in the event of a medical emergency or an AE that necessitates identification of the clinical trial material for the welfare of that subject. Except in a medical emergency, the Investigator (or designee) and blinded clinical site staff will remain blinded during the conduct of the study and until such time that all discrepancies in the clinical database are resolved (ie, at the database lock). The date/initials and reason for the Investigator (or designee) removing the study blind will be documented. Although the Investigator (or designee) will remain blinded as to treatment, the Investigator (or designee) will assess the data in

aggregate for safety and tolerability review. Unblinding for any other reason will be considered a protocol violation.

6.3 Study Restrictions

6.3.1 Diet, Fluid, and Activity Control

Subjects will adhere to recommended dietary and activity restrictions prior to sigmoidoscopy/ biopsy according to the Investigator (or designee).

Subjects will maintain their normal level of physical activity throughout the entire study (ie, will not begin a new exercise program or participate in any unusually strenuous physical exertion). There are no dietary restrictions throughout the study except for fasting for at least 8 hours prior to study visits on Days 0, 28, 84, and 112 (except for dietary requirements that are part of the preparations for a sigmoidoscopy).

6.3.2 Concomitant Medications

Subjects will refrain from participation in any other investigational study drug trial in which receipt of any investigational drug occurred within 5 half-lives or 1 month, whichever is longer, prior to Screening and during the entire study.

Subjects will be expected to continue their existing medication regimen, provided those treatments are permitted in the protocol.

Subjects may be receiving the following drugs at enrolment and must maintain stable doses throughout the treatment and follow-up period:

- Oral 5-ASA therapy may be continued provided that subjects have been on treatment for at least 6 weeks with a stable dose for the 2 weeks immediately prior to screening endoscopy
- Oral corticosteroid therapy (prednisone at a stable dose ≤ 20 mg/day, or equivalent steroid) may be continued provided that subjects have been on treatment for at least 4 weeks with a stable dose for at least 2 weeks immediately prior to screening endoscopy
- Azathioprine or 6-MP may be continued provided that the dose has been stable for the 4 weeks immediately prior to screening endoscopy
- Antidiarrhoeals (eg, loperamide, diphenoxylate with atropine) may be continued at a stable dose for control of chronic diarrhoea

- Probiotics (eg, Culturelle, *Saccharomyces boulardii*) may be continued provided that the dose has been stable for the 2 weeks immediately prior to screening.

The following drugs must be discontinued and may not be used during the study:

- Use of topical 5-ASA or corticosteroid enemas/suppositories must be discontinued within 2 weeks prior to the screening endoscopy
- TNF- α antagonist drugs must not be used within 60 days prior to screening
- Ustekinumab must not be used within 3 months prior to screening
- Cyclosporine, thalidomide, tacrolimus, sirolimus, or mycophenolate mofetil must not be used within 1 month prior to screening
- Investigational drugs or biologic agents must not be used within 1 month (or 5 half-lives) prior to screening
- Vedolizumab, natalizumab, or other biologic therapy must not be used during the study. Subjects with prior treatment with vedolizumab or natalizumab are not eligible for participation in the study.
- No live viral vaccines should be administered within 1 month prior to screening
- Subjects must have discontinued antibiotics for treatment of infection according to the criteria listed in [Section 5.2](#).

The Investigator (or designee) will review all subject medications prior to study entry and consult with the Medical Monitor if any questions or concerns arise. In general, subjects may continue concomitant treatments for stable or controlled concurrent medical conditions.

When concomitant use of a medication is in doubt, an evaluation will be made by the Investigator(s) (or designee[s]) and Medical Monitor to allow on-study use of some medications that are stable and unlikely to interfere with study medications and assessments.

Use of any newly prescribed, intermittent, or as-needed medication taken by a subject during the course of the study and the reason for its use (eg, to address an AE) will be documented in the source documents and the concomitant medication CRF. The administration of any of the disallowed concomitant medications noted above is prohibited.

6.3.3 Contraception

Female participants must be unlikely to conceive according to the criteria listed in [Section 5.1](#).

Females of non-childbearing potential are defined as females who are ≥ 45 years of age with > 1 year since last menses. Female subjects who are of non-childbearing potential will not be required to use contraception.

If a female subject is < 45 years of age, or cessation of menses is < 1 year and > 6 months, FSH must be documented as elevated into the post-menopausal range at Screening or the subject must have been surgically sterile (eg, bilateral oophorectomy, hysterectomy) for at least 90 days.

Women of childbearing potential must have a negative serum pregnancy test at Screening and a negative urine pregnancy test within 24 hours prior to the first dose of study medication in order to receive study drug.

Women of childbearing potential when sexually active with male partners who are not sterile will be required to use adequate hormonal contraception or use appropriate double barrier contraception (such as a combination of male condom with either cervical cap, diaphragm, or sponge with spermicide) as per local regulations and guidelines from the time of signing the ICF until 28 days after the last dose of study drug.

Any subject who becomes pregnant during the study must immediately discontinue further treatment with study drug and will be followed through the pregnancy's outcome (see [Appendix F](#)).

6.4 Screening Procedures (Days -42 to -7)

Subjects will undergo study-specific screening within 42 days prior to dosing (Day 0). Prior to the Screening visit, subjects will have fasted for ≥ 8 hours.

Subjects will sign the study-specific consent form in the presence of a study site physician (or appropriate designee), prior to any screening procedures being performed. The information recorded for all subjects, regardless of their suitability for the study, will be retained and archived.

The following information and procedures will be recorded and performed as part of the screening assessments for the first Screening visit:

- demographic data
- medical history
- prior medications (including all prescription medications within 3 months prior to screening)
- review of inclusion/exclusion criteria
- height and weight
- complete physical examination, including neurological examination; any subject with abnormal neurological examination will be excluded from study participation
- vital signs (including BP, heart rate, respiration rate, and temperature)
- 12-lead ECG
- clinical laboratory evaluations (including haematology, coagulation factors, serum chemistry, and C-reactive protein [CRP]; see [Appendix B](#))
- stool for *C.difficile* (confirmed by toxin result), culture, and ova and parasites
- urinalysis (UA; see [Appendix B](#))
- PML subjective checklist (see [Appendix D](#))
- TB test (QuantiFERON-TB Gold assay or TB skin test) and chest x-ray (if indicated for positive TB test; see [Appendix C](#))
- hepatitis B and C testing
- serum pregnancy test (for WOCBP)

Subjects who meet all of the preceding screening criteria will attend a second Screening visit (however, subjects may have a combined Screening visit that includes endoscopy), where they will undergo:

- sigmoidoscopy and biopsy (within 14 days of randomisation)
- complete Mayo Score assessment (within 14 days of randomisation; see [Appendix A](#)). Eligibility/baseline Mayo Score and sigmoidoscopy/biopsy should be done as close to randomisation as possible. Mayo Score for stool frequency and rectal bleeding should be done before the day of sigmoidoscopy. However, if the subject has a combined Screening visit, then the Mayo Score for stool frequency and rectal bleeding should be done before the day of randomization for final determination of eligibility. Mayo Score for PGA will be completed on the day of the sigmoidoscopy. Sigmoidoscopy should be the last procedure before randomisation. Subjects must meet eligibility criteria of Mayo Score 6 to 12 and endoscopy subscore of ≥ 2 in order to be randomised

- John Cunningham virus (JCV) antibody testing (within 90 days prior to dosing; a sample will be obtained for testing at the second Screening visit in the absence of prior JCV testing).

Subjects will be randomised within 7 days of dosing.

6.5 Clinical Site Admission (Day 0)

6.5.1 Predose Procedures

On arrival at the study site on Day 0, subjects will undergo the following assessments prior to dosing (see [Table 6-1](#)):

- confirmation of eligibility
- prior and concomitant medications
- AEs
- weight
- vital signs
- 12-lead ECG
- directed physical examination
- clinical laboratory evaluations (including haematology, coagulation, serum chemistry [fasting], CRP, and UA; see [Appendix B](#))
- PML subjective checklist (see [Appendix D](#)); subjects will be educated on the signs and symptoms of PML and advised to report to designated site personnel if they experience any of those signs or symptoms at any time during the study
- IBDQ (see [Appendix G](#))
- faecal calprotectin
- urine pregnancy test (for WOCBP; subject must have negative pregnancy test to be dosed)
- PK blood sample (within 2 hours prior to dosing)
- PD blood sample (within 2 hours prior to dosing; at selected sites only)
- ADA testing
- blood sample for exploratory immunologic assessment (selected sites only)
- dose administration (after completion of the preceding procedures); it should be noted that a delay to dosing on Day 0 due to IP shipment delay will not be considered a protocol deviation

6.5.2 Postdose Procedures

Subjects will be observed for up to 4 hours after the first dose of study drug. Following dose administration, the following assessments will be performed in the clinic:

- AEs
- concomitant medications
- vital signs (at 1, 2, and 4 hours \pm 20 minutes postdose)
- directed physical examination (4 hours postdose)
- PK blood sample (1, 2, and 4 hours \pm 20 minutes postdose)
- PD blood sample (4 hours \pm 20 minutes postdose; at selected sites only)

6.6 Clinical Site Visits (Days 14, 28, 42, and 56)

Subjects will be instructed to take the study drug QD, preferably in the morning. Subjects will be instructed not to take their study drug dose the morning of their study site visits to allow for predose blood sampling. On these visits, subjects will take the study drug dose following completion of the blood collection. Details on dosing times and allowable dosing windows will be provided in the pharmacy manual and explained to the subject prior to their dismissal from the study site.

Subjects will return to the study site at designated visits according to the study schedule and will arrive without having taken their dose for the day. *Subjects will have fasted for \geq 8 hours on Day 28 prior to arrival at the study site.* The following assessments will be performed prior to dose administration:

- AEs
- concomitant medications
- weight
- vital signs
- 12-lead ECG (Days 14 and 56 only)
- directed physical examination
- PML subjective checklist (see [Appendix D](#)); any positive responses to the PML subjective checklist will require that the PML objective checklist be performed by the Investigator according to [Appendix D](#) and the study manual
- urine pregnancy test (for WOCBP). Subjects must have negative urine pregnancy test to proceed with dosing
- partial Mayo Score assessment (rectal bleeding, stool frequency, PGA subscores only; see [Appendix A](#))
- PK blood sample (within 1 hour prior to dosing)

- PD blood sample (within 1 hour prior to dosing; selected sites only)
- clinical laboratory evaluations (including haematology, coagulation, serum chemistry, CRP, and UA; see [Appendix B](#)) (Days 14, 28 [fasting], and 56 only)
- ADA testing (Days 28 and 56 only)
- faecal calprotectin (Day 42 only)

6.7 Day 70 (Phone Visit)

Sites will conduct the subject visit by phone.

The following assessments should be performed during this phone visit:

- AEs
- concomitant medications
- recording of rectal bleeding and stool frequency subscores only via diary record (see [Appendix A](#))
- PML subjective checklist (see [Appendix D](#)); any positive responses to the PML subjective checklist will require that the PML objective checklist be performed by the Investigator at the study site according to [Appendix D](#) and the study manual

6.8 Final Treatment Day Clinical Site Visit (Day 84 or Early Termination)

The following assessments should be performed:

- AEs
- concomitant medications
- weight
- vital signs
- 12-lead ECG
- complete physical examination
- clinical laboratory evaluations (including haematology, coagulation, serum chemistry [fasting], CRP, and UA; see [Appendix B](#))
- PML subjective checklist (see [Appendix D](#)); any positive responses to the PML subjective checklist will require that the PML objective checklist be performed by the Investigator according to [Appendix D](#) and the study manual
- serum pregnancy test (WOCBP)
- sigmoidoscopy and biopsy
- complete Mayo Score assessment (rectal bleeding, stool frequency, PGA, and endoscopy subscores; see [Appendix A](#))
- IBDQ (see [Appendix G](#))

- faecal calprotectin
- PK blood sample (within 1 hour prior to dosing and 1, 2, and 4 hours \pm 20 minutes postdose)
- PD blood sample (within 1 hour prior to dosing and 4 hours \pm 20 minutes postdose; at selected sites only)
- ADA testing

Subjects who experience a flare of UC requiring rescue treatment that is prohibited in the protocol (in the judgement of the Investigator) will be discontinued from further treatment with study drug. Subjects who terminate early from treatment may be placed on appropriate therapy by the treating physician. Subjects will complete an Early Termination visit (including endoscopy) within 10 days following discontinuation, undergo the study procedures detailed in the Study Flow Chart ([Table 6-1](#)), and will be encouraged to be followed for all safety assessments through 28 days.

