--	--

	
18. Use of topical 5-ASA or corticosteroid enemas/suppositories within 2 weeks of administration of the screening endoscopy.
 
19. Use of TNF-α antagonists within 60 days prior to screening.
 
20. Use of ustekinumab within 3 months prior to screening.
 
21. Use of cyclosporine, thalidomide, tacrolimus, sirolimus, or mycophenolate mofetil within 1 month prior to screening.
 
22. Have received any investigational or biologic agent within 1 month (or 5 half-lives of the agent, whichever is longer) prior to screening.
 
23. Prior treatment with vedolizumab or natalizumab.

Test Product(s), Dose, and Mode of Administration:
	
Subjects will receive the following treatments according to a randomisation schedule generated by IXRS:
 
 • PTG-100 (150 mg) once daily (QD) by oral administration • PTG-100 (300 mg) QD by oral administration • PTG-100 (900 mg) QD by oral administration • Placebo QD by oral administration 
Matching PTG-100 (150 mg or 300 mg unit dose) and placebo capsules will be provided to subjects in prepackaged individual study drug kits, identical in appearance, according to the randomisation schedule. During the double-blind treatment period, subjects will take a total of 3 capsules QD, as indicated below, without regard to meals.
 
 • 150 mg PTG-100: 1 \times 150-mg capsule, 2 \times placebo capsules • 300 mg PTG-100: 2 \times 150-mg capsules, 1 \times placebo capsule • 900 mg PTG-100: 3 \times 300-mg capsules • Placebo: 3 \times placebo capsules

Duration of Treatment:
	
Planned Enrolment/Screening Duration: up to 42 days (Days -42 to -1). Outpatient Visits: Days 14, 28, 42, 56, and 84. A telephone visit will be conducted on Day 70. Follow-up Visit: approximately 28 days (Day 112) after the last dose of study drug. Planned Study Conduct Duration (Screening to Follow-up visit): approximately 17 to 20 months (up to 42 days of screening + 12- to 15-month enrolment + 12 weeks treatment + 28 days follow-up).

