The schematic of the study design is displayed in Figure 4-2. The start of the study is defined as the date the first subject enrolled in the study (ie, signs an Informed Consent Form [ICF]). A subject who completes the Day 112 Follow-up visit is considered to have completed the study. Completion of the study does not include any unplanned Follow-up visits (eg, return to the clinic for repeat clinical laboratory) or the phone visit approximately 6 months after the end of treatment. The end of the study is defined as the date the last subject completes the study (or completes an Early Termination visit). The planned duration of study conduct is approximately 17 to 20 months from Screening through the final subject's Follow-up visit (up to 42 days of screening + 12- to 15-month enrolment + 12 weeks treatment + 28 days follow-up).

Figure 4-2 Study Design Schematic

Phase 2b in UC patients: 12 Week Induction
Randomised, Double-blind, Placebo-controlled Adaptive Design

ADA = anti-drug antibodies; IBDQ = Inflammatory Bowel Disease Questionnaire; PD = pharmacodynamics; PK = pharmacokinetics; QD = once daily; TNF α = tumour necrosis factor-alpha; UC = ulcerative colitis.

In this study, the primary efficacy endpoint is clinical remission as defined by the rectal bleeding, stool frequency, and endoscopic subscores of the Mayo Score; clinical response, endoscopic response, and endoscopic remission will be determined using designated subscores of the Mayo Score assessment (see [Section 7.4](#) for details). Changes in complete and partial Mayo Score, rectal bleeding subscore, stool frequency subscore, and endoscopic subscore will be evaluated at designated time points. The IBDQ questionnaire will be assessed pre- and post-treatment; sigmoidoscopy and biopsy will be performed at baseline and Day 84 for evaluation of endoscopic response and remission and histological assessment. Stool samples will be collected for faecal calprotectin at designated time points. Subject blood samples will be obtained at designated time points from Day 0 through Day 112 for analysis of safety labs, PK, PD, and ADA parameters.

Safety will be monitored with AE inquiries, assessment of concomitant medication use, clinical laboratory evaluations ([Appendix B](#)), vital sign measurements, 12-lead ECGs, and physical examination findings during the study. A PML assessment will also be done at designated time points. A study flow chart is presented in [Table 6-1](#).

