5.3 Removal of Subjects from Study Participation

In accordance with the Declaration of Helsinki and other applicable regulations, a subject has the right to withdraw from the study at any time and for any reason without prejudice to his or her future medical care by the physician or at an institution. The Investigator (or designee) may remove a subject from the study if, in the Investigator's (or designee's) opinion, it is not in the best interest of the subject to continue the study. Subjects may be withdrawn due to (but not limited to) any of the following:

- change in compliance with inclusion/exclusion criterion that is clinically relevant and affects subject safety
- at the subject's request (withdrawal of consent)
- protocol noncompliance
- occurrence of AEs that, in the Investigator's opinion, require subject removal
- occurrence of pregnancy
- intake of non-permitted concomitant medication that might affect subject safety or study assessments/objectives.

Notification of withdrawal will be made to the Sponsor as soon as is practical. In case of withdrawal, all reasonable efforts will be made to perform all final study day assessments within 10 days of termination (eg, Early Termination visit) ([Table 6-1](#)). The date the subject is withdrawn from the study and the reason for withdrawal will be recorded on the subject's Case Report Form (CRF). All withdrawn subjects will be followed until resolution of all their AEs or until the unresolved AEs are judged by the Investigator (or designee) to have stabilised.

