² Day 70 AE monitoring will be obtained via phone call and data to calculate rectal bleeding and stool frequency subscores will be obtained; 6-month follow-up PML assessment will be obtained via phone call (the phone call should occur 6 months following discontinuation of treatment if the subject terminates early).

³ Procedures to be performed within 10 days of Early Termination.

⁴ All prior medications taken within 3 months before Screening should be recorded.

⁵ Complete physical examinations (including a neurological examination) should be conducted at Screening. Complete physical examinations should also be conducted at Day 84, Day 112, and/or Early Termination. Directed physical examinations should be conducted at other time points. The Day 0 postdose examination will occur 4 hours postdose.

⁶ Participants should be rested in a supine or semi-recumbent position for ≥ 5 minutes prior to recording of ECGs and vital signs. The ECGs and vital signs should be assessed prior to blood draws. Temperature by oral, axillary, or tympanic route may be permitted provided the same route is used for the participant throughout the study.

⁷ Vital signs will be done at 1, 2, and 4 hours ± 20 minutes postdose following the first dose of study drug.

⁸ Predose (baseline) ECGs should be repeated 3 times with 1- to 2-minute intervals between ECG readings, all within 2 hours prior to dosing.

⁹ ECG only to be performed if previously abnormal.

¹⁰ Laboratory samples collected at Screening and on Day 0 (predose), Day 28, Day 84 (or Early Termination), and Day 112 MUST be after the participant has FASTED from all food and drink except water for ≥ 8 hours (except for any dietary requirements that are part of sigmoidoscopy prep). Chemistry Panel at these fasting visits will include cholesterol and glucose analytes. All other non-fasting visits will have Chemistry Panel completed without cholesterol and glucose analytes. See [Appendix B](#) for list of analytes assessed.

¹¹ PML Assessment Questionnaire subjective checklist will be performed at Screening and at designated study visits (see [Appendix D](#)). If the Screening PML subjective checklist was performed within 14 days of Day 0, it will not need to be repeated on Day 0. At Day 0 (predose), subjects will be educated on the signs and symptoms of PML and advised to report if they experience any of those signs or symptoms at any time during the study.

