Three additional tables will present the incidence of treatment-emergent adverse events by PT, treatment-emergent events leading to study withdrawal and treatment-emergent events with a fatal outcome, sorted in the order of frequency for the entire safety population.

All adverse events occurring on study (pre-treatment, treatment, follow-up) will be listed in subject data listings.

By-subject listings also will be provided for the following: subject deaths; serious adverse events; and adverse events leading to withdrawal.

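### New-onset adverse events after stopping drug are sought for at most 10 required days in early terminators against about 28 in completers, and the plan does not say when their AE recording ends

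*Protocol*

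**What the plan says.** **Early terminators.** Protocol 6.8: "Subjects will complete an Early Termination visit (including endoscopy) within 10 days following discontinuation"; beyond that visit they "will be encouraged to be followed for all safety assessments through 28 days". Footnote 3 of Table 6-1 agrees on the timing: "Procedures to be performed within 10 days of Early Termination". Section 5.3 is softer still: "all reasonable efforts will be made to perform all final study day assessments within 10 days of termination".

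**Completers.** The synopsis places the follow-up visit "approximately 28 days (Day 112) after the last dose of study drug". Section 6.9 lists AEs, laboratory tests and a serum pregnancy test at that visit. Section 4.1 allows ±3 days at Day 84 and ±7 days at Day 112. Section 6.3.3 also uses 28 days, for contraception: "from the time of signing the ICF until 28 days after the last dose of study drug".

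**Recording.** Section 6.13.2 records nonserious AEs from Day 0 and SAEs from consent, both up to completion of the study. Section 4.1 defines a subject's completion by the Day 112 visit and gives no counterpart for a subject who never reaches it. Sections 5.3 and 6.13.2 follow AEs already present until they resolve or stabilise.

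**Analysis.** SAP 4.8.1 counts as treatment-emergent an event with onset after dosing, up to the end-of-study visit, and summarises by subject incidence. Protocol Appendix F instead counts any AE reported after a dose, with no end point. SAP section 5 declares no changes from the protocol. SAP 4.8.1 also plans a table of "treatment-emergent events leading to study withdrawal" (Table 14.3.1.8).

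**The concern.** Safety and tolerability is the first primary objective, and every safety endpoint compares a dose with placebo. A subject who stops early has one required contact, at most 10 days after stopping. A completer has a scheduled contact about 28 days after the last dose. A new infection or other event starting in weeks 3 or 4 after stopping has a planned route into the database for a completer but only a voluntary one for an early terminator. The last scheduled pregnancy test shows the same difference.

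If the share of early terminators differs between arms, so does the intensity of the search for new events, and crude incidence carries that difference into the comparison. Because the end of recording is undefined, sites could also handle the same late event differently.

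A separate point concerns the withdrawal table. Section 6.8 distinguishes stopping drug from leaving follow-up. A subject who stops drug for an AE but stays for the encouraged follow-up is not clearly counted in a table built on study withdrawal. Appendix F lists *drug withdrawn* as an action-taken category, yet no table in SAP 7.1 uses it.

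**Working it through.** **Step 1. The plan's own figure.** Follow-up visit day minus last treatment day: 112 − 84 = 28 days. This reproduces the synopsis.

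**Step 2. Completers with visit windows**, taking the last dose at the Day 84 visit:
- shortest: (112 − 7) − (84 + 3) = 105 − 87 = 18 days
- longest: (112 + 7) − (84 − 3) = 119 − 81 = 38 days

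**Step 3. The gap.** Early terminators have at most 10 required days.
- nominal: 28 − 10 = 18 days; 18/28 = 64% of the nominal window has no required contact
- against the shortest completer window: 18 − 10 = 8 days

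The call about 6 months after treatment does not close this. Section 6.10 gives it the PML checklist, and Table 6-1 has no AE entry at Day 252.

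**Step 4. How many new events could be missed (illustration).** The documents give neither the risk of a new AE after stopping nor an early-termination rate, so both are assumed. Let r be the 28-day risk of a new AE, with constant hazard λ = −ln(1 − r)/28. A visit on day 10 captures 1 − exp(−10λ). For r = 10%, λ = 0.00376, the captured risk is 3.69%, and 10 − 3.69 = 6.31 points are missed.

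| Assumed r | Seen by day 10 | Share captured | Missed, points |
|---|---|---|---|
| 5% | 1.82% | 36% | 3.18 |
| 10% | 3.69% | 37% | 6.31 |
| 20% | 7.66% | 38% | 12.34 |
| 30% | 11.96% | 40% | 18.04 |

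These are points among early terminators with no contact after the visit. For a whole arm, multiply by the share d who stop early. Take 75 per arm (the plan expects 70 to 80 in the selected arms) and d from 5% to 20%:
- low end: 75 × 0.05 × 0.0318 = 0.12 subjects, or 0.16 points
- high end: 75 × 0.20 × 0.1804 = 2.71 subjects, or 3.61 points

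Placing the visit on day 10 favours the plan. Assuming that nobody accepts the encouraged follow-up goes against it.

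**Step 5. Which measures can move.** A subject who stopped because of a treatment-emergent AE already counts in the primary safety endpoint (at least one AE), so later events cannot change that subject's status. Step 4 counts any new event, so the effect on the primary safety endpoint is smaller than shown.

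**The case against.** The strongest defence is that safety follow-up of early terminators is not cut off at 10 days. Sections 5.3 and 6.13.2 follow existing AEs until resolved or stable, which covers the event that made a subject stop. Follow-up to 28 days is encouraged, subjects are invited to report AEs at any time, the alert card is kept after discontinuation, and the PML call follows months later. All of this stands, and it limits the point to new-onset events and to their planned ascertainment.

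A reader might infer three stronger things that the documents do not support.
- *That the study, and so AE recording, ends for an early terminator at the termination visit.* The words "or completes an Early Termination visit" belong to the sentence in 4.1 that dates the end of the whole study. For the individual subject the end of recording is undefined, not set at 10 days.
- *That 28 days is a declared risk window.* It is the timing of a visit and the length of a contraception requirement; neither is called an AE risk period. Some completers are also seen as early as 18 days.
- *That the primary safety endpoint is biased in subjects who stop for AEs.* Step 5 shows why not. The shorter window applies to every early terminator, whatever the reason, and a biased comparison would need stopping to differ by arm, which cannot be known from the plan.

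What survives is that voluntary reporting is not equivalent to a scheduled inquiry, and that nothing in either document explains why the two groups differ.

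**Conclusion.** The point holds for new-onset events. Required ascertainment after the last dose is at most 10 days for early terminators against a nominal 28 (18 to 38) for completers. The end of AE recording for early terminators is unstated, the treatment-emergent window varies by subject, and crude incidence does not adjust for it. The exposed measures are new SAEs, AEs of special interest and additional preferred terms; the primary safety endpoint is exposed only in early terminators with no earlier AE.

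Under-counting is possible, not demonstrated. The range of 0.1 to 2.7 subjects per arm of 75 (0.2 to 3.6 points) rests on an assumed 5% to 20% stopping early, an assumed 28-day risk of 5% to 30%, a constant hazard and no uptake of the encouraged follow-up. The upper end needs all the unfavourable values together. This is a cheap improvement worth making, not a flaw that undermines the trial.

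**What to change.** 1. **Protocol 6.8 and Table 6-1:** make the contact 28 days after last dose a planned data-collection point for early terminators. A phone call covering AEs, SAEs, concomitant medication and pregnancy status is enough. The nominal window is then 28 days in both groups.
2. **Protocol 6.13.2:** state that AE recording for early terminators runs to that contact, and reconcile this with the definitions in 4.1.
3. **SAP 4.8.1:** use one treatment-emergent window for all subjects, anchored to first and last dose. It should reach at least 38 days after last dose; a 28 + 7 = 35-day cut-off would drop days 36 to 38, which completers can contribute now. Reconcile it with Appendix F and record the difference in SAP section 5.
4. **Separately, SAP 7.1:** add a table of treatment-emergent AEs with action taken *drug withdrawn*, beside Table 14.3.1.8. Appendix F lists the category; the CRF is not among the documents, so confirm that the field is collected.

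**Cost:** wording in both documents, one extra table, and one phone contact per early terminator: 0.05 × 240 = 12 to 0.20 × 240 = 48 subjects if 5% to 20% stop early (assumed). Reported AE rates may be slightly higher.
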